Most current practice guidelines (i.e. APA, Expert Consensus, Texas Medication Algorithm, German Guideline on Diagnosis and Treatment of Bipolar Disorders) rank lamotrigine as a first-line treatment for acute bipolar depression. This is based on both evidence-based data such as work at NIMH (Frye et al., 2000a), the first industry sponsored trial (Calabrese et al., 1999), and now almost a decade of experience by psychiatrists in the community treating participants with bipolar disorder. The reason that lamotrigine does not have an indication for the acute phase of depression, in contrast to its maintenance indication, is that the 5 industry sponsored studies, with the exception of the 1999 Calabrese trial, have been largely negative or have been judged to be failed studies. However, it has generally been agreed upon that the 5 individual studies were underpowered and may have been compromised by a large placebo response rate. Beyond common sources of variability (i.e. severity of illness and BPI/BPII heterogeneity), the greatest source of variability may likely relate to the fact that the acute depression registration program took more than 10 years to complete. A selection bias as to the characteristics of participants enrolled in these latter negative or failed trials may be relevant.

Nonetheless, a recent meta-analysis by Geddes and colleagues, has addressed the inadequate power issue of the individual studies (Geddes et al., 2009). A meta-analysis of the full ITT trial populations (see clinical trial register for lamotrigine at GSK.com) was conducted with estimates of the relative risks of response (50% reduction in depression rating scale) and remission (<12 on MADRS) using the Mantel-Haenszel fixed effect. Bipolar depressed participants treated with lamotrigine were more likely to respond to treatment than those treated with placebo on both HAM-D (RR=1.27, 95% CI=1.09-1.47, Heterogeneity  $\chi^2=1.80$  (df=4) p=0.772, Test of RR=1: z=3.13 p=0.002) and MADRS (RR=1.22, 95% CI=1.06-1.41, Heterogeneity  $\chi^2=3.12$  (df = 4) p=0.538, test of RR=1: z=2.80 p=0.005). Remission rates were higher on MADRS (pooled RR=1.21, 95% CI=1.03-1.42; Heterogeneity  $\chi^2=5.86$  (df=4) p=0.210 Test of RR=1: z=2.30 p=0.021), but not on the Ham-D (Figure 1). Thus, with a larger sample size, the data is suggestive of an acute antidepressant response with lamotrigine. More

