Selected participants may be asked to have their SCID interview audio/videotaped. These participants would be selected by the investigator and would sign a separate consent allowing permission to be taped. This tape would only be identified with the participant's study identifier and kept in a locked file. The purpose of these tapes would be to be used for inter rater reliability and quality assurance across the multi-site project.

If a participant fulfills all inclusion and exclusion criteria and he/she is not on an antidepressant at the screening visit, can continue directly to the enrollment visit and be randomized.

If the participant was on an antidepressant at the time of the screening visit, he/she is willing to discontinue it and it would be clinically reasonable to stop it, then the antidepressant will be tapered off in 1 week. The participant will have to be at least 7 days completely off the antidepressant before randomization. Then, the total number of days from screening to enrollment for these participants will be 14 days.

Patients enrolling in FLAME will also be given the option to participate in a separate study called 1H-MR Spectroscopy Before and After Treatment with Lamotrigine or Fluoxetine in Bipolar Depression (IRB 13-003660). This study is designed to only recruit subjects who participate in FLAME. This study will be conducted in tandem with FLAME.

Enrollment/baseline/randomization visit (could be at the same day of screening visit)

After consent is obtained and eligibility has been confirmed (inclusion/exclusion criteria; SCID, questionnaire ratings and blood drawn), RAVE® randomization case report form (CRF) will be submitted. Randomization will be done using blocking (blocks of 6 participants), and by study site with RAVE® (License) randomization tool. Block randomization will be utilized to assure balance between the 2 treatment arms. BPI disorder participants, who are randomized to fluoxetine and were not receiving any mood stabilizers at the enrollment visit, will be started on a conventional mood stabilizer just after randomization. These participants should be on a mood stabilizer for at least 7 days before starting study medication.

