### Data Analysis:

We will investigate association between the primary endpoints a set of SNPs in the gene candidates and/or GWA studies to evaluate a greater number of SNPs and bioinformatics tools to perform pathway analysis. Primary analyses will evaluate the association between treatment response and adverse events phenotypes and SNPs in candidate genes by comparing genotype frequencies between the treatment responder and non-responder groups and the presence/absence of adverse events, using logistic regression, assuming a log-additive model for

allele effects. Logistic regression will enable multivariate analyses, and in particular to assess genetic effects on treatment response and adverse events, while adjusting for other possible risk factors, and modeling gene-environment interactions. Covariates modeled in the analysis will include age of onset of bipolar disorder, and presence or absence of circadian rhythm liability, concomitant medication, alcohol abuse or dependence comorbidity (lifetime), stressful events (defined as presence or absence of any stressful event in the last 12 months and as a score that will summarize the number of stressful events in the prior 12 months), binge eating, body mass index measures and other relevant phenotypes.

A large majority of the Mayo Clinic Rochester participant population is white, non-Hispanic. However, due to the greater ethnic diversity of participants at the other sites, we anticipate that approximately 25% of our sample may come from other racial or ethnic groups. Therefore, all of our genetic analyses will be adjusted for self-reported ethnicity and secondary analyses will be undertaken within ethnically homogeneous subgroups.

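### Cheap improvement, not an error: the treatment-response model names neither study site nor baseline depression severity

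*Combined protocol and SAP*

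**What the plan says.** The Data Analysis section specifies logistic regression with a log-additive allele effect, "while adjusting for other possible risk factors, and modeling gene-environment interactions". The covariate list begins "Covariates modeled in the analysis will include age of onset of bipolar disorder, and presence or absence of circadian rhythm liability, concomitant medication", continues with lifetime alcohol comorbidity and stressful events, and ends "binge eating, body mass index measures and other relevant phenotypes". Genetic analyses are also adjusted for self-reported ethnicity. The Endpoints section adds age, gender, treatment history and similar factors as things to be evaluated. Site and baseline severity appear in neither place.

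Elsewhere the protocol uses or records both:

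- **Site.** The enrollment visit text says "Randomization will be done using blocking (blocks of 6 participants), and by study site". Data Analysis itself expects ethnic mix to differ by site ("due to the greater ethnic diversity of participants at the other sites"). The Participant Population table anticipates 400 participants at the Mayo sites and 100 at Lindner.
- **Severity.** Inclusion criterion 3 admits every level of depression from mild upward. Table 1 schedules BISS and CGI-BP at enrollment. The background on lamotrigine lists severity among the usual sources of variation between trials: "Beyond common sources of variability (i.e. severity of illness and BPI/BPII heterogeneity".

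Response is a CGI-BP change rating of 1 or 2 (Psychometrics Testing). The Power Statement gives 80% power for an odds ratio of 2.90 at minor allele frequency 0.2, with 150 responders, 150 non-responders and alpha 0.00005.

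**The concern.** At an alpha of 0.00005 the study can detect only large genetic effects, so power that needs no extra patients is worth having. In logistic regression, adjusting for a variable that strongly predicts the outcome raises the power of the test on another term, even when the two are unrelated. Baseline severity is an obvious candidate. Site could matter because ratings are made by clinicians in an open-label trial, and because the protocol itself links site to ethnic mix. The list names several less obvious covariates and commits to neither of these.

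**Working it through.** **1. The plan's own figure.** Inputs from the Power Statement: N = 300, 50% response, minor allele frequency 0.2, odds ratio 2.90, alpha 0.00005 (two-sided assumed).

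- Model: logit P(response) = a + b·g, with g = 0, 1, 2 risk alleles and b = ln 2.90. Hardy-Weinberg proportions are 0.64, 0.32 and 0.04.
- Setting overall response to 50% gives a = -0.409 and response rates of 39.9%, 65.8% and 84.8%.
- Likelihood-ratio noncentrality = 2N × {E[p ln p + (1-p) ln(1-p)] - ln 0.5} = 2 × 300 × 0.0401 = 24.07.
- Critical value of chi-square (1 df) at 0.00005 = 16.45. Power = 80.2%, so the stated 80% reproduces.

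The second pair in the Power Statement prints an impossible allele frequency (2.35). A frequency of 0.4 reproduces its odds ratio of 2.35 at 80.3%. That pair is not used below.

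**2. Adding severity.** Severity is taken as a standard normal score independent of genotype. Its odds ratio per standard deviation (SD) is an assumption. The marginal SNP odds ratio is held at 2.90. The Aims are stated per drug (200 each), so n = 200 is shown too. Entries are power (%) without and with severity, from 10,000 simulated trials per row. The last two columns give the gain in points from the expected-data formula in step 1.

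| Severity OR per SD | n=300 | n=200 | Formula gain, n=300 | Formula gain, n=200 |
|---|---|---|---|---|
| 1.0 | 81.5, 81.5 | 47.6, 47.6 | 0 | 0 |
| 1.25 | 81.4, 82.0 | 48.2, 49.1 | 0.7 | 0.9 |
| 1.5 | 81.5, 83.8 | 47.9, 50.8 | 2.3 | 2.8 |
| 2.0 | 80.6, 87.0 | 49.2, 57.0 | 5.8 | 7.6 |

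If 2.90 is instead the odds ratio conditional on severity, the gains over severity odds ratios 1.25 to 2.0 are again about 1 to 8 points (n=300: 80.0 to 80.8, 76.3 to 78.6, 67.6 to 75.4).

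**3. Adding site.** The smaller site's share is 100/(400+100) = 20%. With site unlinked to genotype, an assumed 15-point response gap between sites adds 1.2 points (n=300) or 1.0 (n=200). A 30-point gap adds 3.3 or 5.3.

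**4. Cost when both are inert.** With eight or nine other inert covariates already in the model:

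- n=300: 81.0 to 81.0, and in a separate run 81.1 to 80.8 (two sites) or 81.0 (three sites).
- n=200: 48.8 to 49.1. At the per-drug detectable odds ratio of 3.82, 80.5 to 80.2 or 80.3.
- A further run with eight other covariates gave changes of -0.5 to +0.4 points.

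**5. When site is linked to genotype.** Take allele frequency 0.2 at Mayo and 0.3 at Lindner (assumed), n=300.

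- Neither covariate predicts response: 85.6 to 84.2, a loss of 1.4 points.
- Site also predicts response (conditional SNP odds ratio 2.90, marginal 2.79 because severity is given an odds ratio of 1.5): adding site alone moves power from 84.2 to 79.2 at site odds ratio 1.5, and from 75.7 to 79.7 at 0.67.
- The higher unadjusted figure is partly confounding. A SNP with no effect shows an unadjusted odds ratio of 1.04 at site odds ratio 1.5 and 1.07 at 2.

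**6. What the adjusted odds ratio means.** With severity odds ratios of 1.25, 1.5 and 2.0, a marginal 2.90 corresponds to a conditional SNP odds ratio of about 2.9, 3.0 and 3.2. The gain is in the power of the test and not in a smaller standard error.

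**The case against.** The strongest reply is that nothing is broken. The open wording already permits both covariates, and no document says that severity or site predicts response. Response is a change rating, already relative to the patient's earlier state, so severity may predict it weakly. Randomisation by site is an argument for adjusting a treatment comparison, while the primary test is SNP against response. The lamotrigine background discusses variation across trials, puts the long duration of the programme above severity, and names bipolar subtype alongside it. All of this stands. It limits the claim to a cheap improvement with an assumed gain.

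A second reply is that small-sample likelihood-ratio tests run slightly liberal and each added term makes them more so. At nominal 5%, null size moved from 5.5 to 5.7% (n=300) and from 5.7 to 5.9% (n=200). One rough rescaling for this put the loss from three inert terms at 0.5 point for n=300 (77.4 to 76.9) and 1.1 for n=200 (44.8 to 43.7). With 4,000 replicates each such power has a Monte Carlo standard error near 0.8 point (square root of 0.44 × 0.56/4,000). The separate run in step 4, read raw or size-corrected, stayed within half a point, and its gains at severity odds ratios of 1.5 and 2.0 remained 2 to 3 and 6 to 8 points. The conclusion is unchanged.

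A reader might also infer that ancestry control is inadequate. The documents do not show that: the plan says "all of our genetic analyses will be adjusted for self-reported ethnicity and secondary analyses will be undertaken within ethnically homogeneous subgroups". In simulation, genotype-derived components did no better than separately coded ethnicity labels (inflation factor 1.03 to 1.04 against 1.02 to 1.03).

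**Conclusion.** The point holds as a cheap improvement. The response model omits by name a randomisation factor and a recorded baseline value that may predict outcome. Naming them costs little and may raise power.

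The low cost is better supported than the gain. The gain is about 0 points if neither covariate predicts response, 1 to 3 at a severity odds ratio of 1.25 to 1.5 per SD, and 6 to 8 at 2.0. It assumes minor allele frequency 0.2, marginal odds ratio 2.90, alpha 0.00005, n of 200 to 300 and severity independent of genotype. If site is linked to both genotype and response, power can move several points either way, but the adjusted test removes confounding by site.

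Three stronger readings are not supported. The plan does not fall short of its stated 80% for this reason, because that figure reproduces without either covariate. The SNP tests are not shown to be biased: nothing in the documents links severity to genotype, and site is not shown to be a confounder. Nor does naming two covariates by itself prevent others being chosen after results are seen, since the open category remains.

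**What to change.** In Data Analysis, for the treatment-response model only, add study site and one pre-specified baseline severity measure to the named covariates. The BISS depression score at the enrollment visit would serve. Choose one scale and one visit in the text: leaving a choice between BISS and CGI-BP would create a new decision to be made after the data are seen, and patients who taper an antidepressant are rated at both screening and enrollment. State whether the Mayo locations count as one site or two. Report the SNP odds ratio as conditional on these terms.

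Do not carry the two covariates into the rash and antidepressant-induced mania models, where events may be few. The protocol's 5% for discontinuation due to rash would be 0.05 × 200 = 10 events, and its pooled SSRI switch rate of 3.7% would be 0.037 × 200 = 7.4. Its other switch rates run much higher, so no single count can be given.

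The cost is a sentence of text and 2 to 3 degrees of freedom (1 for severity, 1 or 2 for site). No new data are needed.

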**Short title: The FLAME Study**

**Protocol Version/Date:06/17/2016**

**IRB#: 13-003545**

**PI: [name]. and colleagues.**

### **ABSTRACT:**

This study is part of the Mayo Clinic Bipolar Biobank and Biomarker Development (3BD) Program. This project is supported by the Marriott Family and Foundation.

Depression is the predominant prevailing mood state of bipolar disorder and it is associated with substantial morbidity and mortality. However, in comparison to acute mania, bipolar depression is understudied both from the standpoint of its pathophysiology as well as clinical trials and treatment development. Given the lack of evidence-based guidelines, clinicians and participants enter a treatment phase with little guidance.

The FLAME Study is a 16-week, open randomized comparative effectiveness trial evaluating genomic predictors and biomarkers of response and adverse events to treatment with lamotrigine (n=200) and fluoxetine (n=200) for bipolar I, II and schizoaffective bipolar depressed participants. Participants age 18-65; will be invited to take part of this study. Participating sites include: Mayo Clinic, Rochester and Austin and Lindner Center of HOPE in Mason, Ohio.

It is known that functionally significant genetic polymorphisms of pharmacokinetic and pharmacodynamic pathways can influence individual differences in response to specific medications. We propose to evaluate the contribution of these pharmacogenomic variations to lamotrigine and fluoxetine treatment response and adverse events. We will correlate clinical phenotypes of response and adverse events to treatment with genotype and haplotype variations of drug metabolism, neurotransmitter biosynthesis, (metabolism, storage, release, reuptake), receptor and intracellular signaling—that have been previously implicated to either lamotrigine or fluoxetine drug mechanism of action. These initial steps will be complemented with genome-wide analysis (GWA), pathway analysis and other candidate gene studies.

Based on our results we aim to develop a translational treatment algorithm of bipolar depression that may help individualized treatment for bipolar depression. This algorithm for participants could potentially increase the likelihood of successful treatment interventions, deliver the “right treatment, for the right participant at the right time”, and decrease the number of ineffective treatments and/or risk for serious adverse events.

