### **AIMS:**

1. To evaluate the association between genotype and haplotype variations in candidate genes involved in pharmacodynamic and pharmacokinetic pathways of treatment response to lamotrigine (n=200) or fluoxetine (n=200) in bipolar depression. In addition, we aim to perform exploratory analyses of single-nucleotide polymorphisms (SNPs) obtained from GWA studies with drug response phenotypes.
2. To evaluate the association between genotype and haplotype variations in candidate genes involved in pharmacodynamic and pharmacokinetic pathways of drug adverse events to treatment [rash emergence and antidepressant induced mania (AIM+) to lamotrigine (n=200) or fluoxetine (n=200) respectively in bipolar depression. In addition, we aim to perform exploratory analyses of single-nucleotide polymorphisms (SNPs) obtained from GWA studies with drug adverse events phenotypes.

3. To identify blood and brain metabolites associated with treatment response to lamotrigine (n=200) and fluoxetine (n=200) in bipolar depression.

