In addition to the sources of possible pharmacokinetic pharmacogenomic variation mentioned above, pharmacodynamic factors are also a possible source for pharmacogenomic variation in response to these agents. Fluoxetine is an inhibitor of 5-HT reuptake, with the majority of its effect – at least in experimental animals – exerted as a result of its influence on serotonergic neurotransmission. A recent meta-analysis (GENDEP, MARS and STAR\*D Investigators, 2013) of the pharmacogenomics of treatment response, included the 3 largest pharmacogenomic studies of SSRIs found only genotypic trends; meanwhile, an analysis restricted to individuals treated with SSRIs citalopram (STAR\*D) or escitalopram (GENDEP) identified an intergenic region on chromosome 5 associated with early improvement after 2 weeks of treatment. The authors concluded that in order to find stronger genetic associations of treatment response, larger case numbers and homogeneous phenotyping is needed and our study will address both necessities. The 3BD Clinical Program will contribute with a relevant number of participants with a detailed and homogeneous phenotypification (of treatment response, adverse events to treatment, correlation with specific symptoms/symptom change and comorbidity).

Antidepressant-induced mania (AIM+) in bipolar depression is still one of the main concerns when prescribing antidepressants; understanding the genetic risk factors associated with AIM+ would improve clinical care.. Sidor and MacQueen (2009) pooled treatment estimates for 1000 participants and although could not demonstrate a greater risk of AIM+ with antidepressants in general, when they performed analysis by groups of medication, found a risk on switching to mania of 43% for tricyclic antidepressants, 15% for venlafaxine, 7% for SSRIs and 5% for bupropion. Several studies of the potential association between AIM+ and variation in the serotonin transporter gene (SLC6A4) have been completed, focusing primarily on the length polymorphism in the promoter region, known as 5HTTLPR. A meta-analysis performed by our group found no significant evidence of association of the 5HTTLPR long/short variant with risk of AIM (Biernacka et al., 2012) but also identified significant methodological limitations in these studies such as lack of ancestry report, heterogeneity in the selected phenotype, lack of covariate analysis and environmental factors

[figure not shown]

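### Ancestry control in the primary genetic models rests on self-reported ethnicity alone; genotype principal components should be added to it wherever genome-wide data exist

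*Combined protocol and SAP*

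**What the plan says.** Under Statistical Considerations, Data Analysis, the primary analyses are log-additive logistic regressions of treatment response and of adverse events on candidate-gene SNPs. The section notes that most patients at the lead site are white non-Hispanic. It expects more variety in ethnicity elsewhere, and on that ground says: "we anticipate that approximately 25% of our sample may come from other racial or ethnic groups". From this it concludes: "Therefore, all of our genetic analyses will be adjusted for self-reported ethnicity and secondary analyses will be undertaken within ethnically homogeneous subgroups".

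The other named covariates are clinical ("Covariates modeled in the analysis will include age of onset of bipolar disorder", followed by concomitant medication, alcohol comorbidity, stressful events, body mass index and similar items). The list ends open, with an allowance for further relevant phenotypes. Study site is not named. No section mentions principal components, ancestry-informative markers, a mixed model, genomic control or a check of test inflation.

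Genome-wide data are planned. The Abstract says "These initial steps will be complemented with genome-wide analysis (GWA), pathway analysis and other candidate gene studies". Aim 1 says "we aim to perform exploratory analyses of single-nucleotide polymorphisms (SNPs) obtained from GWA studies with drug response phenotypes", and Aim 2 repeats this for adverse events. The Data Analysis section is less firm and offers candidate genes and/or genome-wide work.

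**The concern.** Drug is randomised in this trial, but genotype is not. Any SNP whose frequency differs by ancestry will be associated with any outcome that also differs by ancestry, unless the model accounts for ancestry. A self-reported category cannot represent admixture inside the category, or distinct ancestries that share one label.

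Some planned targets are of the exposed kind. The Lamotrigine pharmacogenomics section describes HLA findings for skin reactions that differ between Han Chinese and European-descended patients, and rash is the lamotrigine adverse-event phenotype. The ancestry mix also differs by site, response is clinician-rated in an open trial, and site is not a named covariate. Rating differences between sites are therefore one plausible link between ancestry and outcome, though the documents do not show that they exist.

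At stake are false or missed associations in a study whose stated aim is a treatment algorithm. A better control can be computed from genotypes that the study already plans to obtain.

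**Working it through.** **Inputs from the documents.** About 25% of participants from other groups (Data Analysis). In the Power Statement: 1000 SNPs, significance level 5×10⁻⁵, 150 responders and 150 non-responders, and 80% power for an odds ratio (OR) of 2.90 at minor allele frequency (MAF) 0.2.

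**The plan's own figure.** The level is 0.05/1000 = 5×10⁻⁵ (two-sided assumed), so the critical z is 4.056. For a likelihood-ratio test, the noncentrality is 2N × [Σ P(g){p ln p + (1−p) ln(1−p)} − ln 0.5], where p is the response probability for genotype g, genotypes are in Hardy-Weinberg proportions, and overall response is 50%. With N=300, OR 2.90 and MAF 0.2 this is 24.07, giving 80.2% power. The stated 80% is reproduced. The 300 matches neither 200 per drug nor 400 in total, so other sizes are shown too.

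**Null SNP, nominal 5% test.** Assumptions not in the documents: individual ancestry proportion follows Beta(1.5, 1.5) in the 25% and Beta(0.3, 5.7) in the majority; response odds change by the ancestry OR per unit of ancestry; the SNP has the two frequencies shown in the two ancestral populations. There are 3000 runs per cell at N=200 and 300, so the Monte Carlo standard error near 5% is √(0.05×0.95/3000) = 0.4 points.

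| Ancestry OR | Frequencies | No adjustment, N=300 | Self-report, N=300 | Self-report + ancestry, N=300 | Self-report, N=200 |
|---|---|---|---|---|---|
| 1 | 0.1/0.3 | 5.3% | 5.2% | 5.1% | 4.8% |
| 1 | 0.1/0.6 | 4.6% | 5.0% | 5.2% | 4.9% |
| 1 | 0.05/0.9 | 4.2% | 4.5% | 4.2% | 5.2% |
| 2 | 0.1/0.3 | 6.0% | 4.9% | 5.5% | 4.7% |
| 2 | 0.1/0.6 | 8.6% | 5.4% | 5.6% | 5.9% |
| 2 | 0.05/0.9 | 15.6% | 6.9% | 4.6% | 5.5% |
| 4 | 0.1/0.3 | 8.0% | 5.2% | 5.0% | 5.2% |
| 4 | 0.1/0.6 | 21.3% | 6.5% | 3.9% | 6.1% |
| 4 | 0.05/0.9 | 45.2% | 12.5% | 5.4% | 8.8% |

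At N=400 and ancestry OR 4 (2000 runs), self-report gives 8.3% at 0.1/0.6 and 14.3% at 0.05/0.9. With ancestry added these are 5.1% and 4.6%.

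**At 5×10⁻⁵, N=300.** There are too few runs to count directly, so the rate is taken as Φ(−(4.056−m)) + Φ(−(4.056+m)), where m is the simulated mean z under self-report adjustment. At ancestry OR 2 and 0.05/0.9, m = 0.40 gives 1.3×10⁻⁴. At ancestry OR 4, m = 0.44 (0.1/0.6) gives 1.5×10⁻⁴ and m = 0.77 (0.05/0.9) gives 5.1×10⁻⁴, about ten times nominal.

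**True OR 2.90, 5×10⁻⁵, N=300 (2500 runs, Wald tests).** These are not comparable with the 80% above, because the test, allele frequencies and covariates differ.

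| Ancestry effect | Frequencies | Self-report: power, median OR | Ancestry added: power, median OR |
|---|---|---|---|
| Opposite (OR 1/4) | 0.1/0.6 | 49%, 2.65 | 59%, 3.00 |
| Opposite (OR 1/4) | 0.05/0.9 | 33%, 2.47 | 41%, 2.98 |
| None | 0.1/0.6 | 64%, 2.93 | 58%, 2.94 |
| None | 0.05/0.9 | 60%, 2.96 | 41%, 2.97 |
| Same direction (OR 4) | 0.1/0.6 | 73%, 3.19 | 54%, 2.96 |
| Same direction (OR 4) | 0.05/0.9 | 73%, 3.39 | 33%, 2.95 |

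In the last two rows, the higher power under self-report comes with an inflated OR.

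**Average over many SNPs.** In a simulated arm of 200, the 25% were given one label, half of them sharing the majority ancestry and half not (Fst 0.1, log-odds shift of 1). Null tests at p<0.05 were 6.0% with self-report and 5.3% with four components added; mean chi-square was 1.09 and 1.03. With clean categories and only gradual admixture the two adjustments were equal (1.01 to 1.03).

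**The case against.** The strongest reply is that the plan already does most of the work. In the extreme scenario self-report cuts the error rate from 45.2% to 12.5%, and subgroup analyses are promised as well. This stands as mitigation. It does not close the point, because the subgroup analyses are secondary, their definition is not given, and nothing in the text deals with admixture within a group.

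Second, a reader might infer that a quarter of the sample will be pooled under one residual label. The plan does not say so. It gives no coding for ethnicity, and several separate categories fit the text equally well. With clean categories the average gain from components vanishes.

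Third, a large single-locus bias is tempting to quote. Take one label covering two equal ancestries with MAF 0.1 and 0.5 that respond at 35% and 65%. The spurious per-allele OR inside that stratum is 1.63 (1.38 at 40% and 60%). But the primary model uses the whole sample. With the majority responding at 50% and a majority MAF of 0.1 to 0.5 (assumed), the adjusted OR falls to 1.26 to 1.13 (1.17 to 1.08 in the milder case). In an arm of 200 at 35% and 65%, the chance of passing 5×10⁻⁵ is then 0.03% to 0.06%, about 6 to 13 times nominal but still small.

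Fourth, one might say that the plan contradicts itself, because its Fluoxetine pharmacogenomics section faults earlier studies for "lack of ancestry report, heterogeneity in the selected phenotype". It does not: this study records ethnicity and adjusts for it. The HLA example also needs care, since the named Han Chinese allele concerns carbamazepine.

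Finally, genotype adjustment is not free. The power loss is shown in the working, and adverse-event models may have few events. The 5% rash discontinuation figure under Possible Risks for study medications implies 0.05×200 = 10 events. The cited SSRI switch rates of 3.7% and 7% imply about 7 and 14, although the community estimate of up to 30% would give 60. This stands, and it shapes the fix.

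**Conclusion.** The point holds as a worthwhile and inexpensive improvement. Self-reported ethnicity is the only stated ancestry control in the primary models, and the planned genome-wide data would support a better one. The residual bias matters only where two conditions meet: the locus is strongly differentiated by ancestry, and ancestry within a self-reported category relates to response or to the adverse event. The documents give no figure for the second condition, so every size here is conditional on assumed values. At N=300 those sizes are roughly 5% to 7% for a nominal 5% test at ancestry OR 2, and up to 12.5% in one deliberately extreme case.

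A reader might infer that the planned associations are generally unreliable, or that self-report should be dropped in favour of components. Neither follows. The average effect is small, and the simulations tested ancestry added to self-report, not in place of it. Because the analysis section leaves genome-wide work optional, literal replacement could also leave a candidate-gene analysis with no ancestry control at all.

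**What to change.** In the Data Analysis section:

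- Keep the adjustment for self-reported ethnicity, and state its categories.
- Wherever genome-wide genotypes exist, add a small number of leading genotype principal components to the primary models, with the number fixed before outcomes are analysed.
- If only candidate genes are typed, retain the self-report adjustment. Going further would need ancestry-informative markers, which is extra genotyping.
- Define the homogeneous subgroups by genetic cluster, and report the genomic inflation factor.
- For adverse-event models with few events, prespecify fewer components or penalised likelihood.

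Where genome-wide typing is done, this costs SAP wording and a routine computation, with no new visit or sample. The statistical price is power at differentiated loci when ancestry does not affect outcome. For OR 2.90 at 5×10⁻⁵ that loss is 6 points at frequencies 0.1/0.6 and 19 points at 0.05/0.9. It should be acknowledged in the plan.
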